### 7.3. Efficacy

Efficacy assessments will be performed at the time points presented in the Time and Events Table (Section 7.1).

Efficacy assessments will include evaluation of all 68 joints for tenderness and 66 joints for swelling to be performed by an independent joint evaluator, VAS (global disease) for the subject and treating physician, health assessment questionnaire – disability index (HAQ-DI – physical function, which includes an item on pain severity in the past week), as well as other Health outcome measures described in more detail in Section 7.10 and laboratory assessments (CRP). Based on these assessments ACR (20, 50 and 70), DAS28(CRP) and the EULAR response will be calculated.

For those subjects in the actigraphy sub-study at participating sites, physical activity levels will be assessed using actigraphy/an accelerometer. RA symptoms will be assessed through the subject completion of a daily RA Symptom and Impact Diary (see Section 7.10).

#### 7.3.1. Joint assessments

The procedure for joint assessments can be found in the SRM.

### **7.3.1.1. Replaced or Fused Joints**

Replaced or fused joint will not be included in joint evaluations. The reason for absence of the evaluations of those joints must be recorded.

### **7.3.1.2. Independent Joint Evaluator**

One or more independent assessors, who have documented experience in performing joint assessments, will be designated at each trial site to perform joint assessments. Preferably the same independent assessor will perform all joint assessment for the same subject throughout the trial. The principal investigator must ensure that the independent joint assessor has documented experience and he/she is adhering to locally accepted and implemented standards. This also applies if the independent joint assessor is replaced during the trial.

The independent joint assessor should have no other contact with the subject during the trial, must not be the treating physician (investigator), should not discuss the subject's clinical status with the subject during the joint assessment nor with other site personnel, and will not be permitted to review the subject's medical records, the eCRF, nor any of the previous joint assessments.

### **7.3.2. Patient's Assessment of Arthritis Pain**

Subjects will assess the severity of their current arthritis pain using a 100 unit visual analog scale (VAS) by placing a mark on the scale between "0" (no pain) and "100" (most severe pain), which corresponds to the magnitude of their pain.

Further details of this assessment are provided in the SRM.

### **7.3.3. Patient's Global Assessment of Arthritis**

Subjects will complete a global assessment of disease activity using the patient global assessment (PtGA) item, a VAS with anchors "0" (very well) to "100" (very poor).

Further details of this assessment are provided in the SRM.

### **7.3.4. Physician's Global Assessment of Arthritis**

Physicians will complete a global assessment of disease activity using the physician global assessment item (PhGA), a VAS with anchors "0" (none) to "100" (extremely active), respectively.

Further details of this assessment are provided in the SRM.

### **7.3.5. DAS Assessments**

The Disease Activity Score (DAS) assessment is a derived measurement with differential weighting given to each component. The DAS 28(CRP) or DAS 28(ESR) will be calculated at each assessment timepoint.

The components of the DAS 28 arthritis assessment include:

- Tender/Painful Joint Count (28).
- Swollen Joint Count (28).
- CRP or ESR.
- Patient's Global Assessment of Arthritis.

Sites/investigators will not have access to ongoing DAS scores, apart from the screening and Day 1 results (needed to confirm eligibility). DAS28(ESR) value on Day 1 will be used to confirm disease activity eligibility by the IRTS before dosing.

### **7.3.6. ACR Assessments**

The American College of Rheumatology's definition for calculating improvement in RA (ACR20) is calculated as a 20% improvement in tender and swollen joint counts and 20% improvement in 3 of the 5 remaining ACR-core set measures: patient and physician global assessments, pain, disability, and an acute-phase reactant. Similarly, ACR50 and 70 are calculated with the respective percent improvement. This efficacy measurement will be made at every study assessment timepoint.

The specific components of the ACR Assessments that will be used in this study are:

- Tender/Painful Joint count (68).
- Swollen Joint Count (66).
- Patient's Assessment of Arthritis Pain.
- Patient's Global Assessment of Arthritis.
- Physician's Global Assessment of Arthritis.
- CRP or ESR.
- Health Assessment Questionnaire – Disability Index (HAQ-DI).

## **7.4. Safety**

Planned time points for all safety assessments are listed in the Time and Events Table (Section 7.1).

### **7.4.1. Screening visit(s)**

- Chest X-ray (PA and lateral, or in accordance with local requirements).
  - if a chest X-ray has been taken within the past 12 weeks that shows no clinically-significant abnormality, and there are no signs or symptoms suggestive of pulmonary disease that would exclude the subject, then a further chest X-ray is not required.

- Baseline chest HRCT for subjects with  $D_{LCO}$  values  $\geq 60\%$  to  $< 70\%$ , and it is recommended that the subject will be reviewed by a local pulmonologist to exclude significant pre-existing respiratory disease.
- Immunogenicity testing.

#### **7.4.2. Study visits**

Subjects will have systematic safety monitoring throughout the study. Additional time points for safety tests (such as vital signs, physical exams and laboratory safety tests) may be added during the course of the study based on newly available data to ensure appropriate safety monitoring.

In addition to routine laboratory assessments, ECG monitoring, and evaluation of adverse events, particular attention will be paid to respiratory events and function given the potential risk associated with targeting GM-CSF and the effects on alveolar macrophages. This may result in the occurrence of the extremely rare condition of PAP, which is characterized by the accumulation of surfactant lipids and protein in the alveolar spaces (with no fibrosis), with resultant impairment in gas exchange, which may lead to increase a risk of secondary pulmonary infections.

All subjects will return for a follow-up visit at 12 weeks after last dose of study medication.

#### **7.4.3. Safety endpoints and other assessments**

- Incidence of AEs/SAEs.
- Incidence of serious infections and opportunistic infections.
  - Pulmonary events (cough, dyspnea, pulse oximetry, spirometry,  $D_{LCO}$ ).
- Lung biomarkers (such as SP-D, KL-6, LDH, cholestenic acid).
- ECG measurements.
- Vital signs.
- Hematological and clinical chemistry parameters.
- Physical examinations.
- Pregnancy test (for women of child-bearing potential).

#### **7.4.4. Adverse Events (AE) and Serious Adverse Events (SAEs)**

The definitions of an AE or SAE can be found in [Appendix 12.4](#).

The investigator and their designees are responsible for detecting, documenting and reporting events that meet the definition of an AE or SAE.

#### **7.4.4.1. Time period and Frequency for collecting AE and SAE information**

- AEs and SAEs will be collected from the start of Study Treatment until the follow-up contact (12 weeks after the last dose of investigational product), at the timepoints specified in the Time and Events Table (Section 7.1).
- Medical occurrences that begin prior to the start of study treatment but after obtaining informed consent may be recorded on the Medical History/Current Medical Conditions section of the eCRF.
- Any SAEs assessed as related to study participation (*e.g.*, protocol-mandated procedures, invasive tests, or change in existing therapy) or related to a GSK product will be recorded from the time a subject consents to participate in the study up to and including any follow-up contact.
- All SAEs will be recorded and reported to GSK within 24 hours, as indicated in [Appendix 12.4](#).
- Investigators are not obligated to actively seek AEs or SAEs in former study subjects. However, if the investigator learns of any SAE, including a death, at any time after a subject has been discharged from the study, and he/she considers the event reasonably related to the study treatment or study participation, the investigator must promptly notify GSK.

NOTE: The method of recording, evaluating and assessing causality of AEs and SAEs plus procedures for completing and transmitting SAE reports to GSK are provided in [Appendix 12.4](#).

#### **7.4.4.2. Method of Detecting AEs and SAEs**

Care will be taken not to introduce bias when detecting AEs and/or SAEs. Open-ended and non-leading verbal questioning of the subject is the preferred method to inquire about AE occurrence. Appropriate questions include:

- “How are you feeling?”
- “Have you had any (other) medical problems since your last visit/contact?”
- “Have you taken any new medicines, other than those provided in this study, since your last visit/contact?”

#### **7.4.4.3. Follow-up of AEs and SAEs**

After the initial AE/SAE report, the investigator is required to proactively follow each subject at subsequent visits/contacts. All SAEs, and non-serious AEs of special interest (as defined in Section 4.7.1) will be followed until resolution, until the condition stabilizes, until the event is otherwise explained, or until the subject is lost to follow-up (as defined in Section 5.4). Further information on follow-up procedures is given in [Appendix 12.4](#).

#### **7.4.4.4. Cardiovascular and Death Events**

For any cardiovascular events detailed in [Appendix 12.4](#) and all deaths, whether or not they are considered SAEs, specific Cardiovascular (CV) and Death sections of the eCRF

will be required to be completed. These sections include questions regarding cardiovascular (including sudden cardiac death) and non-cardiovascular death.

The CV eCRFs are presented as queries in response to reporting of certain CV MedDRA terms. The CV information should be recorded in the specific cardiovascular section of the CRF within one week of receipt of a CV Event data query prompting its completion.

The Death eCRF is provided immediately after the occurrence or outcome of death is reported. Initial and follow-up reports regarding death must be completed within one week of when the death is reported.

Investigators will be required to fill out event specific data collection tools for the following AEs and SAEs:

- Myocardial infarction/unstable angina.
- Congestive heart failure.
- Arrhythmias.
- Valvulopathy.
- Pulmonary hypertension.
- Cerebrovascular events/stroke and transient ischemic attack.
- Peripheral arterial thromboembolism.
- Deep venous thrombosis/pulmonary embolism.
- Revascularisation.

This information should be recorded in the specific cardiovascular eCRF within one week of when the AE/SAE(s) are first reported.

#### **7.4.5. Laboratory and Other Safety Assessment Abnormalities Reported as AEs and SAEs**

Any abnormal laboratory test results (hematology, clinical chemistry, or urinalysis) or other safety assessments (e.g., ECGs, radiological scans, vital signs measurements), including those that worsen from baseline, and felt to be clinically significant in the medical and scientific judgement of the investigator are to be recorded as AEs or SAEs.

However, any clinically significant safety assessments that are associated with the underlying disease, unless judged by the investigator to be more severe than expected for the subject's condition, are **not** to be reported as AEs or SAEs.

#### **7.4.6. AEs of Special Interest**

Please see Section 4.7.1 for a discussion of potential risks with GSK3196165. Adverse events of special interest include:

- Serious infections, including serious respiratory infections.

- Opportunistic infections including TB reactivation.
- Neutropenia.
- Non life-threatening pulmonary changes related to surfactant accumulation.
- PAP.
- Hypersensitivity reactions, including anaphylaxis.
- Injection site reactions.
- Persistent cough or dyspnea.

#### **7.4.6.1. Disease-Related Events and/or Disease-Related Outcomes Not Qualifying as SAEs**

The following have been specified as disease-related events (DREs) for the study:

- Events related to exacerbation of articular/peri-articular manifestations of RA, will not be reported as AEs, and will be recorded in the DRE eCRF.
- Events related to the articular/peri-articular flare up of the disease, and that require hospitalization, will not be reported as SAEs. However, such events must still be recorded in the DRE eCRF.

These DREs will be monitored by an SRT on a routine basis.

NOTE: However, if either of the following conditions apply, then the event must be recorded and reported as an SAE (instead of a DRE):

- The event is, in the investigator's opinion, of greater intensity, frequency, or duration than expected for the individual subject.

OR

- The investigator considers that there is a reasonable possibility that the event was related to treatment with the investigational product.

New onset or worsening of extra-articular manifestations of RA should be reported as AEs/SAEs.

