### **6.5. Blinding**

The study will be double-blind, which means that the investigator and trial staff at site (apart from the unblinded administrator [study co-ordinator or nurse]), subject, and sponsor personnel who are not members of the DRC will be blinded to the trial treatment allocated to each individual subject.

There will be an unblinded administrator (study co-ordinator or nurse) that will prepare and administer the study treatment. A shield (e.g., eye mask or blindfold) will be used during investigational product administration so that subjects are not able to see the

injection volume, syringe size, or any difference in color between GSK3196165 and placebo.

In this Phase 2b study, the DRC (see Section 10.8.1) will have access to unblinded data at a group level, but will not have individual subject level data.

- The investigator or treating physician may unblind a subject's treatment assignment **only in the case of an emergency** OR in the event of a serious medical condition when knowledge of the study treatment is essential for the appropriate clinical management or welfare of the subject as judged by the investigator.
- Investigators have direct access to the subject's individual study treatment.
- It is preferred (but not required) that the investigator first contacts the Medical Monitor or appropriate GSK study personnel to discuss options **before** unblinding the subject's treatment assignment.
- If GSK personnel are not contacted before the unblinding, the investigator must notify GSK as soon as possible after unblinding, but without revealing the treatment assignment of the unblinded subject, unless that information is important for the safety of subjects currently in the study.
- The date and reason for the unblinding must be fully documented in the eCRF

A subject will be withdrawn if the subject's treatment code is unblinded by the investigator or treating physician. The primary reason for discontinuation (the event or condition which led to the unblinding) will be recorded in the eCRF.

- GSK's Global Clinical Safety and Pharmacovigilance (GCSP) staff may unblind the treatment assignment for any subject with an SAE. If the SAE requires that an expedited regulatory report be sent to one or more regulatory agencies, a copy of the report, identifying the subject's treatment assignment, may be sent to investigators in accordance with local regulations and/or GSK policy.

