#### Events NOT meeting definition of an AE include:

- Any clinically significant abnormal laboratory findings or other abnormal safety assessments which are associated with the underlying disease, unless judged by the investigator to be more severe than expected for the subject's condition.
- Signs and symptoms of RA disease activity, *e.g.* joint pain, swelling, erythema, warmth, and stiffness, or expected progression, should not be reported as AEs, unless in the investigator's opinion they are of greater intensity, frequency or duration than

expected for the individual subject.

- Medical or surgical procedure (e.g., endoscopy, appendectomy): the condition that leads to the procedure is an AE.
- Situations where an untoward medical occurrence did not occur (social and/or convenience admission to a hospital).
- Anticipated day-to-day fluctuations of pre-existing disease(s) or condition(s) present or detected at the start of the study that do not worsen.

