#### 12.4.6. Evaluating AEs and SAEs

##### Assessment of Intensity

The investigator will make an assessment of intensity for each AE and SAE reported during the study and will assign it to one of the following categories:

- Mild: An event that is easily tolerated by the subject, causing minimal discomfort and not interfering with everyday activities.
- Moderate: An event that is sufficiently discomforting to interfere with normal everyday activities.
- Severe: An event that prevents normal everyday activities. An AE that is assessed as severe will not be confused with an SAE. Severity is a category utilized for rating the intensity of an event; and both AEs and SAEs can be assessed as severe.
- An event is defined as 'serious' when it meets at least one of the pre-defined outcomes as described in the definition of an SAE.

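### The note in Protocol 7.4.6.1 orders SAE reporting of RA flares with no seriousness condition, contradicting Appendix 12.4 and leaving SAE incidence open to inflation and site-to-site inconsistency

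*Protocol*

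**What the plan says.** Protocol 7.4.6.1 names two kinds of DRE. The first is the ordinary flare: "Events related to exacerbation of articular/peri-articular manifestations of RA, will not be reported as AEs, and will be recorded in the DRE eCRF". The second is a flare that leads to hospital admission, which is kept out of SAE reporting but still goes on the DRE form. A single note follows both: "if either of the following conditions apply, then the event must be recorded and reported as an SAE (instead of a DRE"). The conditions are that the investigator judges the event to be "of greater intensity, frequency, or duration than expected for the individual subject", or considers that "there is a reasonable possibility that the event was related to treatment with the investigational product".

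Appendix 12.4.1 deals with signs and symptoms of RA activity differently. They "should not be reported as AEs, unless in the investigator's opinion they are of greater intensity, frequency or duration than" would be expected in that subject. Appendix 12.4.6 adds: "An event is defined as 'serious' when it meets at least one of the pre-defined outcomes as described in the definition of an SAE", and "An AE that is assessed as severe will not be confused with an SAE". Appendix 12.4.2 lists the qualifying outcomes and allows medical judgement for important medical events.

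SAE incidence is a major secondary safety endpoint (Protocol 3, SAP 2). SAP 4.10.3 tabulates subjects with serious events and SAP 4.10.4 tabulates DREs separately. SAP 4.10.11.1 puts an SAE summary in every DRC package and lists no DRE summary. Under Protocol 6.5, sponsor pharmacovigilance staff "may unblind the treatment assignment for any subject with an SAE".

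**The concern.** The note decides which table a flare enters. Its two conditions measure unexpectedness and suspected causality, not seriousness, and it offers no AE route. Read as written, a flare managed in the clinic that is worse than usual for the subject becomes an SAE. The appendix would make it an AE.

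Both texts are instructions to sites, so identical flares can be classified differently at different sites. SAP 4.9.1.2 expects roughly 70 sites and no adjustment for centre. The result feeds a major secondary safety endpoint and the SAE summary seen by the committee that can stop arms. Each such report also carries the 24-hour SAE reporting duty in Protocol 7.4.4.1 and brings the subject within the Protocol 6.5 provision on unblinding.

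**Working it through.** The documents give no figure to reproduce, so the check is mainly a comparison of texts. Take a flare that needs no admission and meets no outcome in Appendix 12.4.2.

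| Feature of the flare | Protocol 7.4.6.1 note | Appendix 12.4 |
|---|---|---|
| No worse than expected, not thought related | DRE | Not an AE (12.4.1) |
| Stronger, more frequent or longer than expected | SAE | AE (12.4.1), not serious (12.4.2, 12.4.6) |
| As expected, but possibly drug-related | SAE | No relatedness exception in the RA item of 12.4.1; not serious in any case |

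1. **Does the note cover non-hospitalised flares?** Yes. It follows both kinds of DRE and does not limit itself to the second. If it applied only to admitted flares, 7.4.6.1 would give no instruction for an ordinary flare that meets a condition.
2. **Is either condition a seriousness criterion?** No. Appendix 12.4.6 separates intensity from seriousness, whereas the note lets intensity alone produce an SAE.
3. **Is the omission the protocol's usual style?** No. The sentence after the note gives both the AE and the SAE route for extra-articular worsening, and Section 7.4.5 does the same for abnormal test results.
4. **Does the analysis correct it later?** SAP 4.10.2 to 4.10.4 describe no step that re-checks seriousness. Whether the eCRF forces a seriousness criterion at SAE entry cannot be seen from the documents.
5. **Size per event.** With the planned 35 per arm (Protocol 9.2.1.1), one affected subject adds 1/35 = 0.0286, or about 2.9 percentage points, to that arm's SAE incidence. The step changes if arms are dropped or if subjects move to the rescue column.
6. **Number of events and direction between arms.** Neither can be determined. No flare rate is given. SAP 4.10 tabulates safety by actual treatment at the time of the event, so events after escalation count under Rescued Subjects and not under the randomised arm.

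**The case against.** The strongest reply is that Sections 7.4.4 and 7.4.4.1 already send sites to Appendix 12.4 for definitions and evaluation, and that 7.4.6.1 is about events that would otherwise be SAEs. On that view the note merely restores SAE status to admitted flares, and over-reporting is the cautious error. For admitted flares this is right. For the rest, a general pointer does not displace a specific mandatory instruction. At most the reply shows that the effect depends on which text a site follows, and that is itself a source of inconsistency.

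It is also fair that misclassified flares stay visible. SAEs are tabulated by term and listed by subject (SAP 4.10.3), the Medical Monitor reviews all SAEs (Appendix 12.4.3), and the safety review team monitors DREs. This makes the problem detectable but does not correct the endpoint.

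Three stronger readings are tempting, and the documents do not support them.

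- **The effective doses are made to look safer.** A reader might infer this because flares suggest lack of efficacy. But placebo to 135 mg subjects without a EULAR good or moderate response at Week 12 escalate at Week 14, with a second escape at Week 26. Their later flares then leave the randomised column. Subjects on 180 mg have no escape, so non-responders can remain in that column until the Week 38 withdrawal. The direction could weaken or reverse. The relatedness condition is not a measure of efficacy at all.
- **The shift between arms can be quantified.** It cannot. If one assumed flare rates of 2-10% on placebo and low doses and 0-2% on high doses, the difference would span 0 points (2 - 2) to 10 points (10 - 0). Those rates are assumptions with no source in the documents.
- **Affected subjects would be unblinded.** Section 6.5 permits this for pharmacovigilance staff and does not require it. A copy naming the treatment may reach investigators only where an expedited report is required, which mainly concerns the relatedness condition. The withdrawal rule applies to unblinding by the investigator or treating physician.

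**Conclusion.** The contradiction is real and should be corrected. As written, the note can put non-serious flares into SAE incidence and into the DRC's SAE summary, and sites may apply it differently. The size is about 2.9 points per misclassified subject, assuming a denominator of 35. The total and its balance between arms are unknown, so no claim of bias for or against any dose is made. Unblinding is a possible consequence, not an automatic one. The primary endpoint is not directly affected. The conclusion rests on the texts alone and assumes only that some sites follow the specific note over the general definitions.

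**What to change.** Reconcile Section 7.4.6.1 with Appendix 12.4. Keep the two conditions, and reword the note so that a DRE meeting either of them is recorded and reported as an AE, or as an SAE if it meets the definition in Appendix 12.4.2, instead of as a DRE. Add the relatedness condition to the RA item in Appendix 12.4.1 so that the two lists match. In the SAP, count a flare as an SAE only where the SAE definition is met, to the extent that the eCRF records this.

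The cost is a sentence in the protocol, a matching phrase in the appendix, and a line each in the site guidance and the SAP. No extra data are needed if the eCRF already captures seriousness criteria. Flares that are truly serious and exceed expectation or may be related are still reported as SAEs, so no safety information is lost.
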